## 7.5. Analysis of Exploratory Efficacy Variables

Not applicable.

## 7.6. Pharmacokinetic Analyses

The PK calculations will be performed, if appropriate, using commercial software such as WinNonlin® (Pharsight Corporation, Mountain View, CA). Nominal times will be used in all cases, except when the difference between the actual time and nominal time is greater than 5 minutes for samples collected up to 4 hours after administration; in these cases, actual time will be used for PK analysis.

The PK parameters of  $C_{max}$ ,  $t_{max}$ ,  $C_{min}$ , and  $AUC_{0-t}$  (INCAGN01876) will be summarized by part, dose, and study cycle. The log-transformed PK parameters will be compared among dose levels by using a 1-factor analysis of variance. Dose-dependent parameters ( $C_{max}$  and AUC) will be normalized to the lowest common dose before statistical comparisons. Additionally, if sufficient data are available, the dose proportionality of INCAGN01876  $C_{max}$  and AUC will be evaluated statistically by using a power model (eg, AUC =  $\alpha \cdot (dose^{\beta})$ ) or equivalently log (AUC) = log( $\alpha$ ) +  $\beta \cdot log$  (dose), where linear dose proportionality is accepted if  $\beta$  is not significantly different from 1).

If there is a sufficient amount of plasma concentration data from this study, then the data will be analyzed by standard population PK methods using appropriate software (eg, NONMEM). The effect of covariates on PK parameters will be evaluated. The covariates will include, but not be limited to, demographics (age, weight, sex, race), clinical laboratory test values, and concomitant medications.

The relationship between plasma concentrations of INCAGN01876 and the baseline-subtracted change in QTc interval will be explored graphically and analyzed using a linear mixed-effect model.

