- For a 28-day cycle: maximum of 13 cycles

Reference Therapy, Dosage, and Mode of Administration: Not applicable

Study Schedule/Procedures:

Subjects will have regularly scheduled study visits at the clinical site on Day 1 of each cycle. Additional study visits may be required during some cycles to monitor for safety, efficacy, or for PK [REDACTED] evaluations. Study visits are as follows:

- **Screening:** up to 28 days before enrollment. Screening will begin at the time that the subject signs the informed consent and will continue until the date the subject is enrolled in the study (Cycle 1 Day 1).

- **Cycle 1 and Cycle 6:** Day 1, Day 2, and Day 7 (± 1 day).
- **Cycle 2:** Day 1 (± 1 day) and Day 7 (± 1 day).
- **All other treatment cycles:** Day 1 (± 3 days).
- **Efficacy assessments:** Every 8 weeks (± 7 days) for 12 months, and then every 12 weeks (± 7 days) thereafter until disease progression is determined.
- **End of treatment:** ± 3 days.
- **Safety follow-up:** 30 days (+ 7 days) and 60 days (+ 7 days) after end of treatment.

Safety Assessments:

Subjects will have regularly scheduled study visits at the clinical site on Day 1 of every cycle where targeted physical examinations, vital sign collection, ECOG performance status, collection of concomitant medications, and AE assessments will be performed. A 12-lead ECG will be performed at screening, Cycle 1 Day 1, Cycle 2 Day 1, and then Day 1 of **every other cycle** after Cycle 2 (eg, Cycle 4, Cycle 6, Cycle 8). Triplicate ECG measurements will be performed at Screening, Cycle 1 Day 1, and Cycle 6 Day 1, in conjunction with PK assessments. Laboratory assessments will be collected on Day 1 of each cycle, with more frequent blood sample collection during the first and second cycles (Day 1 and Day 7) to evaluate for DLTs. Toxicities will be monitored continuously and will be graded using the NCI CTCAE v4.03 criteria.

On Day 1 of the first 4 cycles (Cycle 1 Day 1, Cycle 2 Day 1, Cycle 3 Day 1, and Cycle 4 Day 1), subjects will be required to stay at the study site for at least 4 hours after infusion of study drug for safety observation. It is recommended that the subject does not leave the site for any reason during the safety observation period. During the safety observation period, subjects will be assessed for the onset of acute AEs.

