^c Screening laboratory assessments must be performed within 7 days of Cycle 1 Day 1. If performed more than 7 days before Cycle 1 Day 1, then the tests must be repeated and eligibility confirmed before study drug administration on Cycle 1 Day 1.

^d A serum pregnancy test will be required for all women of childbearing potential during screening and must be within 72 hours before the first dose of study drug.

^e Urine pregnancy tests will be conducted as medically indicated or per country-specific requirements.

Table 9: Schedule of Pharmacokinetic [REDACTED] Assessments

Visit Day (Range)	Protocol Section	Timing of Assessment	Screening	Treatment											Post-Treatment
				C1			C2	C3	C4	C6			C7	C8 & C12	Safety Follow-Up Visit 1
				D1	D2	D7	D1	D1	D1	D1	D2	D7	D1	D1	
Evaluation/Window			Day -28 to -1		24 h	± 1 day	± 1 day	± 3 days	± 3 days	± 3 days	24 h	± 1 day	± 3 days	± 3 days	30 days (+ 7 days)
Pharmacokinetic Assessments^a															
Serum sample for PK	7.8	Table 13		X	X	X	X	X	X	X	X	X	X		

^a All PK assessments will be performed by a central laboratory. Details regarding PK samples including specimen handling, processing, and shipping will be outlined in the laboratory manual.

[figure not shown]

Table 10: Local Laboratory Tests: Required Analytes

Serum Chemistry	Hematology	Other
Albumin Alkaline phosphatase Alanine aminotransferase Aspartate aminotransferase Bicarbonate Blood urea nitrogen Calcium Chloride Creatinine Glucose Lactate dehydrogenase Phosphorus Potassium Sodium Total bilirubin Direct bilirubin (If total bilirubin is elevated above ULN) Total protein Uric acid Amylase Lipase	Complete blood count, including: 
 • Hematocrit • Hemoglobin • Mean corpuscular volume • Platelet count • Red blood cell count • White blood cell count Differential count, including: 
 • Basophils • Eosinophils • Lymphocytes • Monocytes • Neutrophils Absolute values must be provided for the following WBC differential laboratory results: 
 • White blood cells • Lymphocytes • Neutrophils 	Hepatitis Hepatitis B surface antigen Hepatitis B core antibody HBV-DNA Hepatitis C virus antibody HCV-RNA
		Pregnancy Test^a Female subjects of childbearing potential only require a serum test at screening. Pregnancy tests (serum or urine) should be repeated if required by local regulations.

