7.8. Pharmacokinetic Assessments

7.8.1. Blood Sample Collection

Pharmacokinetic [REDACTED] samples will be obtained at the visits indicated in [Table 9](#). Timing of PK [REDACTED] assessments are outlined in [Table 13](#). After the predose PK sample is drawn, subjects will begin the study drug infusion. Predose is defined as within 24 hours before administration of study drug. Adjustments to the timing of blood sampling may be made based on emerging PK data. The exact date and time of each PK blood draw will be recorded in the eCRF. Instructions for sample preparation and shipping will be provided in the Laboratory Manual.

Table 13: Timing of Pharmacokinetic [REDACTED] Sample Collection

Study Visit	Assessment	Timing of Sample Collection
Cycle 1 Day 1	PK [REDACTED]	• Preinfusion
	PK	• Postinfusion (\pm 10 min) • 4 h (\pm 30 min) postinfusion
Cycle 1 Day 2	PK	• 24 h (\pm 60 min) postinfusion
Cycle 1 Day 7	PK	• Untimed PK sample
Cycle 2 Day 1	PK	• Preinfusion
Cycle 3 Day 1	PK [REDACTED]	• Preinfusion
Cycle 4 Day 1	PK	• Preinfusion
Cycle 6 Day 1	PK [REDACTED]	• Preinfusion
	PK	• Postinfusion (\pm 10 min) • 4 h (\pm 30 min) postinfusion
Cycle 6 Day 2	PK	• 24 h (\pm 60 min) postinfusion
Cycle 6 Day 7	PK	• Untimed PK sample
Cycle 7 Day 1	PK	• Preinfusion
[REDACTED]	[REDACTED]	[REDACTED]

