APPENDIX C. PHARMACOKINETIC ANALYTICAL PARAMETERS

C_{ave}	Average steady-state plasma concentration ($AUC_{0-12h}/12h$ or $AUC_{0-24h}/24h$)
C_{max}	Maximum observed plasma concentration
C_{min}	Minimum observed plasma concentration during the dosing interval
T_{max}	Time to maximum plasma concentration
AUC_{0-t}	Area under the single-dose plasma concentration-time curve from Hour 0 to the last quantifiable measurable plasma concentration, calculated by the linear trapezoidal rule for increasing concentrations and the log trapezoidal rule for decreasing concentrations
$AUC_{0-\tau}$ (ie, AUC_{0-12h} or AUC_{0-24h})	Area under the steady-state plasma concentration-time curve over 1 dosing interval (ie, from Hour 0 to 12 for BID administration or from Hour 0 to 24 for QD administration), calculated by the linear trapezoidal rule for increasing concentrations and the log trapezoidal rule for decreasing concentrations
λ_z	Apparent terminal phase disposition rate constant, where λ_z is the magnitude of the slope of the linear regression of the log concentration versus time profile during the terminal phase
$t_{1/2}$	Apparent plasma terminal phase disposition half-life (whenever possible), where $t_{1/2} = (\ln 2) / \lambda_z$
Cl/F	Oral dose clearance
V_z/F	Apparent oral dose volume of distribution
Fluctuation	Steady-state fluctuation ($(C_{max} - C_{min})/C_{ave}$)

In addition, the following PK parameters may be calculated, whenever possible, for each subject:

A_e	Amount of drug excreted in the urine over sampling interval
Cl_r	Renal clearance, where $Cl_r = A_e/AUC$
% Excreted or f_e	percent excreted in the urine, where % Excreted = $100 (A_e/\text{dose})$

Pharmacokinetic calculations will be performed, if appropriate, using commercial software such as WinNonlin[®] (Pharsight Corporation, Cary, NC). Additional details of analyses will be described in the statistical analysis plan.

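### AUC0-t has no named closing sample for Cycle 1 or Cycle 6, and PK draws after 4 hours keep nominal times despite windows of 1 to 3 days

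*SAP*

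**What the plan says.** SAP 7.6 sets the time rule: "Nominal times will be used in all cases, except when the difference between the actual time and nominal time is greater than 5 minutes". That exception reaches only draws made within the first 4 h of dosing, which are then analysed at their true times. Protocol 7.8.2 has the same rule. Every later sample therefore stays at its nominal time.

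The later PK draws are the 24 h sample (± 60 minutes, Table 13), Day 7 of Cycles 1 and 6, and the predose samples. Table 9 attaches visit windows to the row "Serum sample for PK": ± 1 day for Day 7, ± 1 day for Cycle 2 Day 1 and ± 3 days for Cycle 7 Day 1. The Synopsis agrees, but Protocol 6.2 gives ± 3 days for Day 1 of every cycle. Table 13 describes the Day 7 draw as "Untimed PK sample" and gives no nominal hour. Protocol 7.8.1 lets a predose sample fall up to 24 h before the dose. It also says: "The exact date and time of each PK blood draw will be recorded in the eCRF".

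Protocol Appendix C defines AUC0-t as "Area under the single-dose plasma concentration-time curve from Hour 0 to the last quantifiable measurable plasma concentration". The SAP's abbreviation list also stops at the last quantifiable concentration, but describes it as being across all of a subject's treatments rather than after a single dose. SAP 7.6 says the PK parameters "will be summarized by part, dose, and study cycle". It then compares log-transformed parameters among doses by one-factor ANOVA and fits a power model for dose proportionality. The only dosing-interval AUC in Appendix C is written for 12 h or 24 h dosing.

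**The concern.** An AUC that runs to the last quantifiable value covers whatever interval the subject happens to supply. In Cycle 1 that could be Day 7 or the Cycle 2 predose draw; in Cycle 6 it could be Day 7 or the Cycle 7 predose draw. Two analysts could close the same cycle differently. Subjects in one summary could also close differently, because one has a quantifiable next predose value and another has none. If low doses fall below the assay limit sooner, the closing time would vary with dose, and the dose-proportionality slope would absorb the difference. The public text does not give the assay limit, so this last point is conditional.

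The time rule is a separate and smaller matter. It corrects a 6-minute deviation at 4 h and leaves a 3-day deviation at the Cycle 7 predose draw uncorrected, although the true time is in the eCRF.

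**Working it through.** The documents give no figure for AUC error, so there is nothing to reproduce first.

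**Inputs from the documents.** Sampling times and windows as above; linear trapezoid for rising and log trapezoid for falling concentrations (Appendix C); 14-day cycle, 14 × 24 = 336 h.

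**Assumptions.** Relative concentration C(t) = 0.4·2^(−t/24) + 0.6·2^(−t/(24T)), with t in hours and terminal half-life T = 5, 10 or 20 days; Day 7 at 144 h; next predose at 336 h; deviations uniform within the windows; no assay error. None of these values is in the public text.

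**1. Closing sample.** For T = 10:
- C(24) = 0.7598, C(144) = 0.4021, C(336) = 0.2274.
- 0–4 h: 3.90; 4–24 h: 17.02.
- 24–144 h: 120 × (0.7598 − 0.4021)/ln(0.7598/0.4021) = 67.45.
- 144–336 h: 192 × (0.4021 − 0.2274)/ln(0.4021/0.2274) = 58.85.
- AUC0-144h = 88.37 and AUC0-336h = 147.22; ratio 0.60.

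For T = 5 and 20 the ratio is 0.71 and 0.54. The longer interval thus gives 1/0.71 = 1.4 to 1/0.54 = 1.9 times the AUC. Across other profiles (half-life 3 to 21 days, one- or two-phase decline) the factor is 1.22 to 2.06.

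**2. Possible effect on the slope.** Suppose exposure is truly proportional to dose (slope 1), and the lowest k of the eight dose levels close at Day 7 while the rest close at the next predose. With x = ln(dose), the slope becomes 1 + ln(ratio) × Σ(x − x̄ over the lowest k)/Σ(x − x̄)². For k = 1 and T = 10: 1 + (−0.51)(−3.63)/37.0 = 1.05. For k = 1 to 3 it is 1.03–1.07 (T = 5), 1.05–1.10 (T = 10) and 1.06–1.12 (T = 20).

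**3. Timing error in one subject.** Take T = 10 and Cycle 6, with Day 7 drawn 24 h late and the Cycle 7 predose 72 h late. C(168) = 0.3725 and C(408) = 0.1847 are then placed at 144 h and 336 h. The two late segments become 120 × 0.3873/0.7129 = 65.2 and 192 × 0.1878/0.7015 = 51.4. The total is 137.5 against 147.2, an error of −6.6%.

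**4. Timing error over the windows** (200,000 draws; SD of log AUC against the on-time AUC; T = 5 / 10 / 20 days):

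| Closing sample | Nominal rule | Actual times only | Actual times, fixed interval |
|---|---|---|---|
| Cycle 2 predose, ± 1 day | 0.035 / 0.021 / 0.012 | 0.012 / 0.022 / 0.029 | 0.005 / 0.005 / 0.005 |
| Cycle 7 predose, ± 3 days | 0.045 / 0.029 / 0.017 | 0.036 / 0.066 / 0.088 | 0.005 / 0.005 / 0.005 |
| Day 7 | 0.027 / 0.016 / 0.009 | 0.058 / 0.073 / 0.082 | 0.008 / 0.010 / 0.010 |

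If Protocol 6.2's ± 3 days applies to Cycle 2 Day 1, the second row also describes Cycle 1. Adding accumulation from five earlier doses leaves the nominal Cycle 6 values at 0.0449 / 0.0297 / 0.0172. With the predose allowance included (uniform, 0 to 24 h early), the nominal rule shifts the mean by +0.4% to +1.0% in Cycle 1 and +0.5% to +1.2% in Cycle 6.

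**5. Group level.** An assumed 30% between-subject CV is a log SD of √ln(1.09) = 0.2936. With the largest noise, √(0.2936² + 0.0449²)/0.2936 = 1.012. With the smallest, √(0.2936² + 0.012²)/0.2936 = 1.001. Total SD rises by 0.1% to 1.2%.

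**The case against.** The best defence of the time rule is that it fixes the interval. Every subject's AUC is labelled as ending at the same hour, and step 4 shows that actual times alone are often worse. That stands: it is why actual times must be paired with a fixed interval, and a reader who infers that switching to actual times is the cure would be wrong.

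A second defence is that the cycle definition settles the closing sample. SAP 4.1.5 ends Cycle 1 after 14 calendar days and starts later cycles at their Day 1 visit, and Table 13 labels the next predose draw with the next cycle's number. A reader could therefore close at Day 7. This is a possible reading, but neither document applies it to AUC0-t, and both AUC definitions point to the last quantifiable value instead. If Day 7 does close, the gain from the remedy is clear at a 5-day half-life (0.027 to 0.008), modest at 10 days (0.016 to 0.010) and absent at 20 days. It cannot be said without condition that the remedy removes most of the timing noise.

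Third, assay error is left out. With an assumed 10% concentration error, the Cycle 1 SD is 0.057 to 0.067 under the nominal rule and about 0.056 with the remedy, when the next predose closes. The improvement in a real individual AUC is smaller than the table suggests.

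The safeguards do not answer the point. The pharmacokineticist's review in SAP 5.3.5.1 identifies subjects to exclude, and Listing 2.7.4 displays sampling times. Neither changes the time used or names the closing sample. The 12 h and 24 h wording in Appendix C spoils no planned result, since that AUC is not an endpoint. It matters only because no usable fixed-interval AUC is defined for 14-, 21- or 28-day cycles.

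**Conclusion.** The point holds as a minor, inexpensive improvement. The unnamed closing sample is the larger part: a factor of about 1.4 to 1.9 in AUC0-t under the assumed half-lives of 5 to 20 days, which makes subjects or dose levels closed at different samples non-comparable. The slope distortion in step 2 would occur only if low doses become unquantifiable earlier, which the public text can neither confirm nor exclude.

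The timing rule adds avoidable noise to individual AUCs: a log SD of 0.012 to 0.045 and a mean shift of up to about 1.2% if the next predose closes. It barely changes group summaries. All of this rests on the assumed profile, half-lives and between-subject CV.

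A reader might infer that the choice of dose is compromised. The documents do not support that. Protocol 4.1.2 lists PK as one of several inputs to a joint decision, SAP 3.3 calls all analyses exploratory, and no dose decision is tied to AUC0-t. Nor does the time rule alter Cmax or Cmin values, which are observed concentrations that a time label does not change.

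**What to change.** Adopt as one package in SAP 7.6, Protocol 7.8.2 and Appendix C:

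- **(a) Fixed interval.** For dose comparisons, calculate AUC over one fixed dosing interval (to Day 14 for 14-day cycles, and to the corresponding day for 21- or 28-day cycles). Close it with the next predose sample, interpolated or log-linearly extrapolated to the nominal end. State how a subject without that sample is handled.
- **(b) Actual times.** Use actual elapsed times from the eCRF for all noncompartmental and population PK calculations. Keep nominal times for summary tables and mean plots, or where an actual time is missing.
- **(c) Definitions.** Replace the 12 h/24 h dosing-interval AUC in Appendix C to match (a), align the two AUC0-t definitions, and give Day 7 a nominal time.

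Do not adopt (b) without (a). The cost is a few sentences in each document and one row of Appendix C. The draw times are already collected, so no new data are needed.

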## 8. SAFETY AND TOLERABILITY

Sample data displays are provided in Appendix A.

#### 8.1. General Considerations

Summary tables may be replaced with listings when appropriate. For instance, an AE frequency table may be replaced with a listing if it only contains a few unique PTs reported on relatively few subjects. Data from the Part 1 portion will be summarized separately where appropriate. Additional summaries for specific subgroups may be included on an ad hoc basis.

Unless otherwise stated, table summaries will be limited to AEs occurring within 60 days of the last administration of study drug.

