6. STUDY ASSESSMENTS

All study assessments will be performed as indicated in the schedule of assessments (see [Table 7](#)) and all laboratory assessments will be performed as indicated in [Table 8](#) and [Table 9](#). [Table 10](#) presents a summary of clinical laboratory analytes to be assessed. See [Section 7](#) for instructions on each assessment. Further details of study procedures and assessments can be found in the Study Reference Manual or applicable procedural documentation.

Table 7: Schedule of Assessments

Visit Day (Range)	Protocol Section	Screening Day -28 to -1	Treatment ^a				Post-Treatment ^b		
			Cycle 1 and Cycle 2		All Subsequent Cycles	Every 8 weeks	EOT	Safety Follow-Up Visit 1	Safety Follow-Up Visit 2
			Day 1	Day 7	Day 1	Disease Status			
Evaluation/Window				± 1 day	± 3 days	± 7 days	± 3 days	30 days (+ 7 days)	60 days (+ 7 days)
Administrative procedures									
Informed consent	7.1	X							
Inclusion/exclusion criteria	3.1, 3.2	X	X						
Contact IWRS	7.2	X	X		X		X		
Medical and cancer history	7.3	X							
Prior/concomitant medications	7.4	X	X	X	X		X	X	X
Administer INCAGN01876	5.2.1		X		X				
Poststudy anticancer therapy status	7.5							X	X
Clinical procedures/assessments									
Comprehensive physical examination (including height)	7.6.2.1	X							
Targeted physical assessment	7.6.2.2		X	X	X		X	X	X
Vital signs and weight	7.6.3	X	X ^c	X	X		X	X	X
ECOG performance status	Appendix D	X	X	X	X		X	X	X
Laboratory assessments	7.6.5	X	X ^d	X	X		X	X	X
12-lead ECG ^e	7.6.4	X ^{f,g}	X ^g		X ^{g,h}		X	X	
AE assessment	7.6.1	X	X	X	X		X	X	X
Efficacy measurements									
Radiologic tumor assessments	7.7	X ⁱ				X ^j	X ^k		X ^k

^a Treatment cycles will begin every 14 days (± 3 days). Alternate dosing schedules may also be explored based on emerging safety, PK data.

^b The mandatory safety follow-up visits should be conducted approximately 30 days and 60 days after the last dose of study drug or before the initiation of a new anticancer treatment, whichever comes first.

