6.4. Follow-Up

6.4.1. Safety Follow-Up

The safety follow-up period is the interval between the EOT visit and the scheduled follow-up visit, which should occur 30 days (+ 7 days) and 60 days (+ 7 days) after the EOT visit (or after the last dose of study drug if the EOT visit was not performed). Adverse events and SAEs must be reported up until at least 60 days after the last dose of study drug, the date of the follow-up visit, or until toxicities resolve, return to baseline, or are deemed irreversible, whichever is

longer. If a subject is scheduled to begin a new anticancer therapy before the end of the 30-day or the 60-day safety follow-up period, then the safety follow-up visit should be performed before new anticancer therapy is started.

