8.3.2. Reporting

Every SAE, regardless of suspected causality (eg, relationship to study drug(s) or study procedure or disease progression), occurring after the subject has signed the ICF through the last study visit (or 60 days after the last dose of study drug, whichever is later) must be reported to the sponsor (or designee) within **24 hours** of learning of its occurrence, unless otherwise specified by the Protocol. Any SAEs occurring more than 60 days after the last dose of study drug should be reported to the sponsor or its designee only if the investigator suspects a causal relationship to the study drug.

Information about all SAEs is collected and recorded on the Adverse Event form of the eCRF. The investigator must assess and record the causal relationship of each SAE to the study treatment.

The investigator must also complete the Incyte Serious Adverse Event Report Form, in English, and send the completed and signed form to the sponsor or designee within 24 hours of becoming aware of the SAE. The investigator must provide a causality assessment, that is, assess whether there is at least a reasonable possibility that the SAE is related to the study treatment: suspected (yes) or not suspected (no). Refer to the Incyte Reference Guide for Completing the Serious Adverse Event Report Form.

The contact information of the sponsor's study-specific representatives is listed in the investigator manual provided to each site. The original copy of the SAE Report Form and the confirmation sheet must be kept at the study site.

Investigational site personnel must report any new information regarding the SAE within 24 hours of becoming aware of the information in the same manner that the initial SAE Report Form was sent. Follow-up information is recorded on an amended or new SAE Report Form, with an indication that it is follow-up to the previously reported SAE and the date of the original report. The follow-up report should include information that was not provided on the previous SAE Report Form, such as the outcome of the event (eg, resolved or ongoing), treatment provided, action taken with study drug because of the SAE (eg, dose reduced, interrupted, or discontinued), or subject disposition (eg, continued or withdrew from study participation). Each recurrence, complication, or progression of the original event should be reported as follow-up to that event, regardless of when it occurs.

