8.8. Immune-Related Adverse Events

Adverse events of a potential immunologic etiology or irAEs may be defined as an AE consistent with an immune phenomenon associated with drug exposure after all other etiologies have been eliminated. Immune-related AEs may be expected based on the nature of INCAGN01876, its mechanism of action, and reported experience with other immunotherapies. Special attention should be paid to AEs that may be suggestive of potential irAEs. An irAE can occur shortly after the first dose or several months after the last dose of treatment. Guidance for the assessment, diagnosis, and management of irAEs is provided in [Section 5.4.7](#) and [Appendix B](#). Suspected irAEs should be discussed with the medical monitor when possible.

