### 8.2. Adverse Events

#### 8.2.1. Adverse Event Definitions

A TEAE is any AE either reported for the first time or worsening of a pre-existing event after first dose of study drug. Analysis of AEs (as discussed below) will be limited to TEAEs, but data listings will include all AEs regardless of their timing in relation to study drug administration.

Adverse events will be tabulated by MedDRA PT and SOC. Severity of AEs will be graded using the National Cancer Institute CTCAE. The CTCAE version 4.03 is used for this study. The CTCAE reporting guidelines and grading details are available on the Cancer Therapy Evaluation Program website.

The subset of AEs considered by the investigator to be related to study drug will be considered to be treatment-related AEs. If the investigator does not specify the relationship of the AE to study drug, the AE will be considered to be treatment-related. The incidence, frequency, duration, and severity of AEs and treatment-related AEs will be tabulated. In addition, SAEs will also be tabulated.

A grading (severity) scale is provided for each AE term. If the toxicity is not included in the CTCAE v4.03 criteria, it will be rated on a scale of 1 to 4 as follows: 1 = mild, 2 = moderate, 3 = severe, and 4 = life threatening. All toxicities will be graded based on the worst level reached, not the level they may have reached if they had not been treated. When the intensity of an AE changes over time for a reporting period (eg, between visits), each change in intensity will be collected as an AE until the event resolves. Only the worst grade will be reported in AE summaries. Also, the Grade 3 or higher AEs will be reported in a listing.

Any missing onset date, causality, or severity must be queried for resolution. Unresolved missing causality and severity will be handled according to the following rules:

- An unresolved missing causality will be considered treatment-related.
- An unresolved missing severity will be identified as an unknown severity.

For purposes of analysis, all AEs will be considered TEAEs unless the AE can unequivocally be defined as not treatment-emergent.

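### SAP 8.1 stops the adverse event tables 60 days after last dose, short of the protocol's own collection period and with no provision for late immune-related events; the safety-visit anchor and the SAE period also need reconciling

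*SAP*

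**What the plan says.** **Table window.** SAP 8.1: "Unless otherwise stated, table summaries will be limited to AEs occurring within 60 days of the last administration of study drug". Neither SAP 8.2 nor the Appendix A shells state an exception for any event type.

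**Event definition and listings.** Protocol 9.4.2.1 and SAP 8.2.1 define a treatment-emergent event by its start or worsening after first dose, with no upper time limit. SAP 8.2.1 adds: "For purposes of analysis, all AEs will be considered TEAEs unless the AE can unequivocally be defined as not treatment-emergent". It also says that "data listings will include all AEs regardless of their timing in relation to study drug administration".

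**Collection.** Protocol 8.1.2 makes 60 days after last dose a minimum for monitoring new events. Protocol 6.4.1 runs reporting to the longest of three limits: at least 60 days after last dose, the follow-up visit, or resolution of toxicities.

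**Visit timing.** Protocol 6.4.1 describes a scheduled follow-up visit "which should occur 30 days (+ 7 days) and 60 days (+ 7 days) after the EOT visit", with last dose as the fallback only when no EOT visit took place. The Synopsis also counts from end of treatment. Table 7 footnote b instead places the same visits "approximately 30 days and 60 days after the last dose of study drug". Table 7 marks an AE assessment at both safety visits.

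**Late immune-related events.** Protocol 5.4.7 and 8.8: "An irAE can occur shortly after the first dose or several months after the last dose of treatment".

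**SAE period.** Protocol 8.3.2 first says that every SAE, whatever its suspected cause, "through the last study visit (or 60 days after the last dose of study drug, whichever is later) must be reported to the sponsor". It then narrows this to events with a suspected link to the drug: "Any SAEs occurring more than 60 days after the last dose of study drug should be reported to the sponsor or its designee only if" such a link is suspected.

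**The concern.** Adverse event frequency, duration and severity form the primary endpoint, so the AE tables are the study's primary result. The SAP cuts them at a point earlier than the mandatory visit at which events are still being assessed. It makes no provision for the delayed toxicity that the protocol names as a feature of this drug class.

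Two protocol inconsistencies bear on the same window. The visit anchor decides how long the gap is. The two SAE sentences decide which serious events reach the sponsor after Day 60. Without a reconciled text, sites could reasonably act differently on the same event.

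**Working it through.** The plan gives no figure for this gap, so there is nothing to reproduce. The check is day-count arithmetic followed by a comparison of the texts.

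**Inputs**
- Table cut-off: Day 60 after last dose (SAP 8.1).
- Visit 2: 60 to 67 days after its anchor (Protocol 6.4.1 and Table 7, window +7 days).
- Interval from last dose to EOT: not given anywhere. Protocol 6.3 says only that the EOT visit follows permanent discontinuation. I assume 0 to 28 days, using the three cycle lengths in Protocol 5.2.1 (14, 21 and 28 days) as cases and leaving out the ±3-day EOT window.

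**Formulae**
- Visit 2 day after last dose = EOT lag + 60 to 67.
- Days collected but not tabulated = Visit 2 day − 60.

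| Anchor and assumed EOT lag | Visit 2, days after last dose | Days outside the tables |
|---|---|---|
| Last dose (Table 7 footnote b) | 60-67 | 0-7 |
| EOT, lag 0 | 0 + 60 to 67 = 60-67 | 0-7 |
| EOT, lag 14 | 14 + 60 to 67 = 74-81 | 14-21 |
| EOT, lag 21 | 21 + 60 to 67 = 81-88 | 21-28 |
| EOT, lag 28 | 28 + 60 to 67 = 88-95 | 28-35 |

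Protocol 6.4.1, 7.5 and Table 7 footnote b bring a safety visit forward when new anticancer therapy is about to start. If that puts Visit 2 on or before Day 60, there is no gap for that subject.

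**Late immune-related events.** If several months is read as 3 to 6 (an assumption), onset is at 3 × 30.4375 ≈ Day 91 to 6 × 30.4375 ≈ Day 183. All of that range is outside the tables under either anchor, and nearly all of it is after Visit 2 even in the longest case above (Day 95). Moving the cut-off to Visit 2 would therefore not capture most such events.

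**SAE sentences.** Take a subject whose last study visit is Visit 2 on Day 67, with an SAE on Day 61.
- Suspected related: reportable under both sentences. No conflict.
- Not suspected related: reportable under the first sentence, because the last visit is later than Day 60, but not under the second. The sentences give opposite answers.

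**The case against.** The strongest case for the SAP is that a fixed 60-day window is a respectable choice. Sixty days is the protocol's minimum monitoring period for new events, and also the routine limit for recording concomitant medication (5.6). After that, ascertainment depends on each subject's visit timing. Protocol 5.6.3 prohibits no therapy in follow-up, so later events may reflect other drugs. An open-ended event definition can coexist with a limited table window. All of this stands as a reason for having some limit. It does not explain a limit that falls short of a mandatory AE assessment, and the SAP offers no reason of its own.

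Several stronger readings are tempting and are not supported:
- *Late events are lost, or the tables are demonstrably biased downward.* They remain in the all-AE listing and in dedicated listings for SAEs, Grade 3 or higher events, fatal events, deaths and immune-related events. SAP 8.1 allows ad hoc summaries. The Kaplan-Meier analyses in SAP 8.2.5 are not expressly cut at Day 60. The number of affected events is unknown and may be small.
- *The typical patient has a gap of two to five weeks.* That needs an EOT lag of 14 to 28 days. Protocol 6.3 allows EOT to coincide with a regular visit, and Table 4 allows up to 28 days for a Grade 3 toxicity to resolve before discontinuation, so such lags are plausible. No document sets or describes a usual lag, however.
- *Follow-up to resolution widens the gap.* That limb concerns toxicities already present; an event that began by Day 60 is tabulated.
- *Any late SAE might go unreported, throughout disease follow-up.* Only unrelated SAEs are in doubt. Table 7 marks no AE assessment in its disease-status column, so it is unclear whether those imaging contacts count as study visits for this purpose.

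On the SAE sentences, the first ends by allowing for other protocol provisions, so the second could be read as an exception. On that reading, extending the period to the later date would have no effect for unrelated SAEs after Day 60. The text therefore still needs reconciling.

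**Conclusion.** The point holds as a mismatch of windows affecting how the primary safety endpoint is tabulated, not as a loss of data.
- AEs starting between Day 60 and Visit 2 are collected but left out of the AE summary tables. The floor is 0-7 days, from the visit window alone. The figures of 14-21, 21-28 and 28-35 days rest entirely on the assumed EOT lags.
- Immune-related events starting after Day 60 have no planned place in the AE summary tables, although the protocol says that they can occur.
- The anchor for the safety visits is contradictory: EOT in Protocol 6.4.1 and the Synopsis, last dose in Table 7 footnote b. Visit 2 cannot be taken as uniformly timed from EOT.
- Section 8.3.2 is contradictory for unrelated SAEs after Day 60, with certainty only up to Visit 2.

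This should be corrected. The likely effect on reported counts is modest, but the tables concerned are the main ones.

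**What to change.** **SAP 8.1.** End the main AE table window at the later of 60 days after last dose and Safety Follow-Up Visit 2. Add a separate summary of immune-related events, treatment-related SAEs and fatal events that start after that window. Keeping it separate avoids a main table whose window depends on causality or outcome. Its footnote should say that late nonserious events are incompletely ascertained and that follow-up differs between subjects.

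**Protocol.** Reconcile the safety-visit anchor across the Synopsis, Table 7 footnote b and Section 6.4.1. Reconcile the two sentences in Section 8.3.2 into one SAE reporting period, stating whether it covers unrelated events after Day 60 and which contacts count as study visits.

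**Cost.** Wording changes in both documents, one changed condition in the AE programs and one small extra summary. No new visits are needed. Reported late AE counts may rise slightly.
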